#### **4.3 TREATMENT COMPLIANCE**

Compliance will be monitored by either administration of all trial medication in the study centre under supervision of the investigating physician or a designee or during ambulatory periods by daily phone contact (e.g. text message) between study site and subject. The measured plasma concentrations of trial medication will provide additional confirmation of compliance.

Subjects who are non-compliant (for instance, who do not appear for scheduled visits or violate trial restrictions) may be removed from the trial and the CRF will be completed accordingly (for further procedures, please see [Section 3.3.4.1](#)).

## 5. ASSESSMENTS

### 5.1 ASSESSMENT OF EFFICACY

Not applicable.

### 5.2 ASSESSMENT OF SAFETY

#### 5.2.1 Physical examination

At screening, the medical examination will include demographics, height and body weight, smoking and alcohol history, relevant medical history and concomitant therapy, review of inclusion and exclusion criteria, review of vital signs (BP, PR), 12-lead ECG, laboratory tests (including drug screening and pregnancy test in females), and a physical examination. At the end of trial examination, it will include review of vital signs, 12-lead ECG, laboratory tests (including pregnancy test in females), and a physical examination including determination of weight.

#### 5.2.2 Vital signs

Systolic and diastolic blood pressures (BP) as well as pulse rate (PR) or heart rate (heart rate is considered to be equal to pulse rate) will be measured by a blood pressure monitor (Carescape VC150, GE Medical Systems) at the times indicated in the [Flow Chart](#), after subjects have rested for at least 5 min in a supine position. All recordings should be made using the same type of blood pressure recording instrument on the same arm, if possible.

#### 5.2.3 Safety laboratory parameters

For the assessment of laboratory parameters, blood and urine samples will be collected by the trial site at the times indicated in the [Flow Chart](#) after the subjects have fasted for at least 10 h. For retests, at the discretion of the investigator or designee, overnight fasting is not required.

The parameters that will be determined are listed in [Tables 5.2.3: 1](#) and [5.2.3: 2](#). Reference ranges will be provided in the ISF, Section 10.

Table 5.2.3: 1 Routine laboratory tests

Functional lab group	BI test name [comment/abbreviation]	A	B	C
Haematology	Haematocrit	X	X	X
	Haemoglobin	X	X	X
	Red Blood Cell Count/Erythrocytes	X	X	X
	Reticulocytes, absol.	X	X	X
	White Blood Cells/Leucocytes	X	X	X
	Platelet Count/Thrombocytes (quant)	X	X	X
Automated relative WBC	Neutrophils/Leukocytes; Eosinophils/Leukocytes; Basophils/ Leukocytes; Monocytes/Leukocytes; Lymphocytes/Leukocytes	X	X	X
Manual differential WBC (if automatic relative WBC is abnormal and considered clinically relevant by the investigator), according to local procedure	Neut. Poly (segs); Neut. Poly (segs); Neutrophils Bands; Neutrophils Bands; Eosinophils/Leukocytes; Eosinophils; Basophils/ Leukocytes; Basophils; Monocytes/ Leukocytes; Monocytes; Lymphocytes/Leukocytes; Lymphocytes.			
Coagulation	Activated Partial Thromboplastin Time Prothrombin time – INR (International Normalization Ratio)	X	X	X
Enzymes	AST [Aspartate transaminase] /GOT, SGOT	X	X	X
	ALT [Alanine transaminase] /GPT, SGPT	X	X	X
	Alkaline Phosphatase	X	X	X
	Gamma-Glutamyl Transferase	X	X	X
	Glutamate Dehydrogenase (GLDH)	X	X	X
	Creatine Kinase [CK]	X	X	X
	Creatine Kinase Isoenzyme MB [only if CK is elevated]	X	X	X
	Lactic Dehydrogenase	X	X	X
	Lipase	X	X	X
Hormones	Amylase (total)	X	X	X
	Thyroid Stimulating Hormone	X	--	--
Substrates	Glucose (Plasma)	X	X	X
	Creatinine	X	X	X
	Bilirubin, Total	X	X	X
	Bilirubin, Direct	X	X	X
	Protein, Total	X	X	X
	Albumin	X	X	X
	C-Reactive Protein (Quant)	X	X	X
	Uric Acid	X	X	X
	Cholesterol, total	X	X	X
	Triglyceride	X	X	X

Table 5.2.3: 1

Routine laboratory tests (cont.)

Functional lab group	BI test name [comment/abbreviation]	A	B	C
Electrolytes	Sodium Potassium Calcium	X X X	X X X	X X X
Urinalysis  (Stix)	Urine Nitrite (qual) Urine Protein (qual) Urine Glucose (qual) Urine Ketone (qual) Urobilinogen (qual) Urine Bilirubin (qual) Urine haemoglobin (qual) Urine WBC/Leucocytes (qual) Urine pH	X X X X X X X X	X X X X X X X X	X X X X X X X X
Urine sediment  (microscopic examination if haemoglobin, leukocytes nitrite or protein are abnormal in urine)	Only positive findings will be reported (for instance, the presence of sediment bacteria, casts in sediment, squamous epithelial cells, erythrocytes, leukocytes)			

A: parameters to be determined at Visit 1 and Visit 2 screening examination, Day -11

B: parameters to be determined at Visit 3 on Day 1, 14, 28 for Dose Group 1 and 2,

parameters to be determined at Visit 3 on Day 1, 7 for Dose Group 3

(for time points refer to [Flow Chart](#))

C: parameters to be determined at Visit 4 (end of trial examination)

The tests listed in [Table 5.2.3: 2](#) are exclusionary laboratory tests that may be repeated as required. The results will not be entered in the CRF/database and will not be reported in the CTR. Except for drug screening, it is planned to perform these tests during screening only. Drug screening will be repeated throughout the study (see [Flow Chart](#)).

Proprietary confidential information © 2020 Boehringer Ingelheim International GmbH or one or more of its affiliated companies

Table 5.2.3: 2      Exclusionary laboratory tests

Functional lab group	Test name
Drug screening (urine)	Amphetamine/MDA Barbiturates Benzodiazepine Cannabis Cocaine Methadone XTC Opiates Phencyclidine Tricyclic antidepressants Alcohol
Infectious serology (blood)	Hepatitis B surface antigen (qualitative) Hepatitis B core antibody (qualitative) Hepatitis C antibodies (qualitative) HIV-1 and HIV-2 antibody (qualitative)
Pregnancy test (serum)	Beta human chorionic gonadotropin (beta-HCG)
Postmenopausal Status (blood)	FSH, estradiol

The results of the drug screening and alcohol test will not be included in the CTR.

The laboratory tests listed in [Table 5.2.3: 1](#) and [5.2.3: 2](#) will be performed at the safety laboratory of 

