3	14	312:00	08:00	Drug administration Dispense of study medication Discharge	x 	x 		x 	x 
	15	336:00	08:00	Drug administration 					
	16	360:00	08:00	Drug administration 					
	17	384:00	08:00	Drug administration 					
	18	408:00	08:00	Drug administration 					
	19	432:00	08:00	Drug administration 					
	20	456:00	08:00	Drug administration 					
		462:00	14:00	Admission to trial site	x 				x
	21	480:00	08:00	Drug administration Dispense of study medication Discharge		x 		x 	x 
	22	504:00	08:00	Drug administration 					
	23	528:00	08:00	Drug administration 					
	24	552:00	08:00	Drug administration 					
	25	576:00	08:00	Drug administration 					
		582:00	14:00	Admission to trial site Start of hospitalisation	x 				x
	26	600:00	08:00	Drug administration					
	27	624:00	08:00	Drug administration					
	28	648:00	08:00	Drug administration	x 	x 		x 	x 
		648:30	08:30						
		650:00	10:00	Light breakfast 					
		652:00	12:00	Lunch 					
		656:00	16:00	Snack (voluntary) 					
		658:00	18:00	Dinner 					
		660:00	20:00					x	x
	29-39	670:00 - 920:00	06:00			x 			x 
			07:25				▲		
			08:00	Drug + tyramine administration 					
			08:30			x		x	
			09:00					x	
			10:00			x		x	
			12:00	Lunch  , discharge from trial site as soon as TYR30 achieved		x	▼		x
			16:00	Snack (voluntary) 				x	
4	41 to 51			End of trial (EoTrial) examination 	x	x		x	x

1. Subject must be informed and written informed consent obtained prior to starting any screening procedures. Screening procedures include physical examination, check of vital signs, ECG, safety laboratory (including drug screening and pregnancy test in females), demographics (including determination of body height and weight, smoking status and alcohol history), relevant medical history, concomitant therapy and review of inclusion/exclusion criteria.

Proprietary confidential information © 2020 Boehringer Ingelheim International GmbH or one or more of its affiliated companies

2. The time is approximate; the procedure is to be performed and completed within the 3 h prior to drug administration.

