3. If several actions are indicated at the same time, the intake of meals will be the last action.
4. At the end of trial visit the EoTrial examination includes physical examination, body weight, vital signs, ECG, safety laboratory (including pregnancy test in females), recording of AEs and concomitant therapies.
5. Only drug and alcohol screening in urine will be done at this time.
6. AEs and concomitant therapies will be recorded throughout the trial, but will be specifically asked for at the times indicated in the [Flow Chart](#) above.
7. From Day -11 to Day -2 escalating oral doses of tyramine from 10 to 700 mg /day will be administered. Baseline blood pressure prior to tyramine dosing defined as three consecutive measurements with a maximum range of 10 mmHg or, if a stable SBP will not be obtained within the 35 minutes, the mean of all 7 readings. Blood pressure monitoring continues 5 minutes after tyramine administration and approximately every 5 minutes thereafter for at least 2 hours and then approximately every 15 minutes for an additional 2 hours. Tyramine dose escalation is to be terminated when the predefined target elevation in SBP is reached (i.e., SBP increased  $\geq$ 30 mmHg from baseline for three consecutive measurements). Participants who do not attain the predefined target elevation in SBP within 4 hours after the maximum tyramine dose (700 mg) on Day -2 or TYR30 is  $<$  200 mg are screening failures. All other participants are going to be included in the study.
8. From Day 29 to Day 39 escalating oral doses of tyramine from 5 to 700 mg /day will be administered in Dose Groups 1 and 2 (concomitantly with BI 1467335 or placebo). The treatment is to be terminated once the participant reaches the predefined target elevation in SBP (i.e., SBP increased  $\geq$ 30 mmHg from baseline for 3 consecutive measurements), and then the participant is allowed for discharge after an overnight stay at trial site.
9. On Days 2 to 6, 8 to 13, 15 to 20 and 22 to 25, subjects are allowed to take their study medication at home if deemed appropriate by the investigator. Compliance of medication intake will be monitored by subject diary and daily phone contact (e.g. text message) between subject and site. The scheduled time for drug intake throughout the study for subjects assigned to Dose Group 1 and 2 (BI 1467335 or placebo) is 08:00 (applies for intake at home and at the trial site).

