4	21 to 31			End of trial (EoTrial) examination 	x	x		x	x

1. Subject must be informed and written informed consent obtained prior to starting any screening procedures. Screening procedures include physical examination, check of vital signs, ECG, safety laboratory (including drug screening and pregnancy test in females), demographics (including determination of body height and weight, smoking status and alcohol history), relevant medical history, concomitant therapy and review of inclusion/exclusion criteria. .
2. The time is approximate; the procedure is to be performed and completed within the 3 h prior to drug administration.
3. If several actions are indicated at the same time, the intake of meals will be the last action.
4. At the end of trial visit the EoTrial examination includes physical examination, body weight, vital signs, ECG, safety laboratory (including pregnancy test), recording of AEs and concomitant therapies.
5. Only drug and alcohol in urine screening will be done at this time.
6. AEs and concomitant therapies will be recorded throughout the trial, but will be specifically asked for at the times indicated in the [Flow Chart](#) above.
7. From Day -11 to Day -2 escalating oral doses of tyramine from 10 mg to 700 mg /day will be administered. Baseline blood pressure prior to tyramine dosing defined as three consecutive measurements with a maximum range of 10 mmHg or, if a stable SBP will not be obtained within the 35 minutes, the mean of all 7 readings. Blood pressure monitoring continues 5 minutes after tyramine administration and approximately every 5 minutes thereafter for at least 2 hours and then approximately every 15 minutes for an additional 2 hours. Tyramine dose escalation is to be terminated when the predefined target elevation in SBP is reached (i.e., SBP increased  $\geq$ 30 mmHg from baseline for three consecutive measurements). Participants who do not attain the predefined target elevation in SBP within 4 hours after the maximum tyramine dose (700 mg) on Day -2 are screening failures. All other participants are going to be included in the study.

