### **4.1.3 Method of assigning subjects to treatment groups**

Subjects will be allocated to treatment sequences prior to the first administration of trial medication in the morning of Day 1 (Visit 3). For this purpose, numbers of the randomisation list will be allocated to the subjects. Subjects are then assigned to a treatment sequence according to the randomisation list.

The randomisation list will be provided to the trial site in advance.

Once a subject number has been assigned, it cannot be reassigned to any other subject.

The randomisation procedure is described in [Section 7.6](#).

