- Prior to allocation of a subject to a treatment into a clinical trial, there must be documented evidence in the source data (e.g. medical records) that the trial participant meets all inclusion criteria and does not meet any exclusion criteria. The absence of records (either medical records, verbal documented feedback of the subject or testing conducted specific for a protocol) to support inclusion/exclusion criteria does not make the subject eligible for the clinical trial.

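### The only pregnancy test assigned before dosing is 13 to 31 days old at the first dose; add one to the Day -1 admission urine

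*Protocol*

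**What the plan says.** **When pregnancy is tested.** Footnote 1 of both flow charts and Section 5.2.1 include a pregnancy test in the screening examination, which the charts place at Visit 1, Day -31 to -13. Table 5.2.3: 2 lists serum beta-HCG as an exclusionary test. The text above that table says these tests "are exclusionary laboratory tests that may be repeated as required", then: "Except for drug screening, it is planned to perform these tests during screening only". Footnote 4 and Section 5.2.1 also require a test at the end-of-trial visit.

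**What is done between Visit 1 and the first dose.**
- The key to Table 5.2.3: 1 defines column A as "parameters to be determined at Visit 1 and Visit 2 screening examination, Day -11". That table holds the routine tests and has no beta-HCG.
- Footnote 5 governs the Day -1 admission sample. The BI 1467335/placebo chart reads "Only drug and alcohol screening in urine will be done at this time"; the phenelzine chart reads "Only drug and alcohol in urine screening will be done at this time".
- The Day 1 draw is column B of Table 5.2.3: 1, again without beta-HCG.

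**What must be known before allocation.** Section 4.1.3 places allocation on the morning of Day 1. Section 8.3.1 asks that, before allocation, there be "documented evidence in the source data (e.g. medical records) that the trial participant meets all inclusion criteria and does not meet any exclusion criteria". Exclusion criterion 28 covers pregnancy itself as well as a positive test. The toxicology text in Section 1.2.1 says the embryo-fetal data support dosing in humans of non-childbearing potential. It admits women of childbearing potential only after a negative test and with two contraceptive methods.

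**The concern.** Section 1.2.1 sets two conditions for women of childbearing potential: a negative test and contraception. Contraception is required throughout, but the negative result available when dosing starts may be a month old. A pregnancy too early to show at Visit 1, or one that begins during the off-site days before the Day -1 admission, would not be found by any assigned test before the first dose. The next assigned test is at the end of the trial, after up to 39 days of BI 1467335 or up to 19 days of phenelzine. The rule in Section 3.3.4 that stops dosing on pregnancy works only once the pregnancy is known.

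The protocol already repeats other checks close to dosing: drug screening on Day -1 and routine laboratory tests on Day 1. Pregnancy is not among them. Section 1.2.1 concerns BI 1467335 only; for the phenelzine group the same need follows from exclusion criterion 28.

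**Working it through.** **Day numbering.** The flow charts show Day -1 at 14:00 as -18:00 h relative to the first dose on Day 1 at 08:00. From 14:00 to 08:00 the next morning is 18 h, so Day -1 directly precedes Day 1 and there is no Day 0. A Day 0 would give -42 h, which does not match. The same numbering reproduces the printed 582:00 h for Day 25 at 14:00 and 670:00 h for Day 29 at 06:00.

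**Age of the test at the first dose of trial medication (Day 1).** With no Day 0, the distance from Day -d to Day 1 is d days.

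| Test | Status in the readable text | Age at first dose |
|---|---|---|
| Visit 1, Day -31 | assigned (earliest) | 31 days |
| Visit 1, Day -13 | assigned (latest) | 13 days |
| Visit 2, Day -11 | permitted, not assigned | 11 days |
| Day -1, 14:00 | proposed | 18 h |

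**Off-site time between the Visit 1 test and the Day -1 admission.**
- Visit 1 to the Day -12 admission: 31 - 12 = 19 days at most, 13 - 12 = 1 day at least.
- Visit 2 discharge to Day -1, BI 1467335/placebo: the baseline tyramine doses of 10, 25, 50, 100 and 200 mg fall on Days -11, -10, -9, -8 and -7. Footnote 7 of this chart makes a TYR30 below 200 mg a screening failure, so the earliest discharge of an eligible subject is Day -7. That gives 7 - 1 = 6 days at most. The latest discharge is Day -2, giving 1 day.
- Visit 2 discharge to Day -1, phenelzine: footnote 7 of that chart has no such floor, so discharge can be on Day -11. That gives 11 - 1 = 10 days at most, 1 day at least.
- Totals: BI 1467335/placebo 1 + 1 = 2 to 19 + 6 = 25 days; phenelzine 1 + 1 = 2 to 19 + 10 = 29 days.
- After a Day -11 test only the second stretch counts: 1 to 6 days, or 1 to 10 days.

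Check at the upper end: for BI 1467335/placebo, 19 off site + 5 in clinic (Day -12 to -7) + 6 off site + 1 (Day -1 to Day 1) = 31 days, the full test age.

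**Interval between the two assigned tests (Visit 1 to end of trial).** From Day -d to Day D is d + D - 1 days.
- BI 1467335/placebo (end of trial Day 41 to 51): 13 + 40 = 53 to 31 + 50 = 81 days.
- Phenelzine (Day 21 to 31): 13 + 20 = 33 to 31 + 30 = 61 days.

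**Number of women at full enrolment.** The Synopsis requires at least 30% of each sex in each dose group.
- Minimum: 0.3 × 24 = 7.2, so 8 in each of two groups; 0.3 × 14 = 4.2, so 5. Total 8 + 8 + 5 = 21.
- Maximum: (24 - 8) × 2 + (14 - 5) = 41.

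The share of childbearing potential is not given, so these counts are upper limits on the number of women to be tested.

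**The case against.** **No rule is broken.** Section 1.2.1 asks for a negative test without setting its age, and the Visit 1 test satisfies that. This stands, and it makes the point an improvement to the plan rather than a breach.

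**A retest is already possible.** Section 5.2.3 lets the test be repeated, and Section 8.3.1 with criterion 28 gives the investigator a reason to do so. Visit 2 is part of screening, so a Day -11 test fits the text. This is correct, but nothing schedules or triggers a repeat, and footnote 5 points against one on Day -1.

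**Contraception covers much of the interval.** Inclusion criterion 5 requires oral contraceptives to start at least 30 days before trial medication, with a condom, and some women will be sterilised, abstinent or postmenopausal. So the off-site days are not a measure of conception risk. Section 1.2.1 nevertheless asks for a negative test in addition to contraception.

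**The fix has limits.** A Day -1 urine test cannot exclude a very recent conception; the 18 hours is the age of the sample, not the period ruled out. It also comes after the baseline tyramine doses, which start on Day -11. Both limits stand. Neither is a reason to rely on the older result when up to 39 days of dosing begin.

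**The off-site counts depend on the flow charts.** The Synopsis and Section 5.6.1 put the baseline challenge on Days -10 to -1, which would move these counts by at most a day. The 200 mg floor appears only in the BI 1467335/placebo footnote 7; without it that group's range would equal phenelzine's, 2 to 29 days. The 13-to-31-day test age depends on neither.

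**The public copy is incomplete.** Footnotes 11 and 12 of the BI 1467335/placebo chart and footnote 11 of the phenelzine chart are not visible. The readable safety-laboratory entries carry only markers 2, 5 and 10, all visible, so none points to a hidden pregnancy test.

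**Conclusion.** The concern holds. Followed as written, the plan allocates and doses women on Day 1 with one assigned pregnancy result, 13 to 31 days old, after 2 to 25 (BI 1467335/placebo) or 2 to 29 (phenelzine) days off site. The upper ends are extremes that require screening on Day -31 and the earliest possible Visit 2 discharge.

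This is a change that should be made on participant-safety grounds. It is not an internal contradiction in the plan and has no bearing on the TSF analysis. It rests on the flow-chart day numbering, on the readable parts of the charts, and on first dose meaning the first dose of BI 1467335, placebo or phenelzine. SAP Section 4 records that the trial was stopped early, so the point concerns the protocol as a plan. Confidence is medium, because of the hidden footnotes and the unknown number of women of childbearing potential.

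**What to change.** 1. In Section 5.2.3 and Table 5.2.3: 2, add a urine pregnancy test for women of childbearing potential at the Day -1 admission (14:00). The table now lists only a serum test.
2. In footnote 5 of both flow charts, except the Day -1 entry from the restriction to drug and alcohol screening. The same footnote marks other admissions, so the exception should name Day -1.
3. State that a negative result must be documented before allocation and before the first dose on Day 1 (08:00).
4. As a separate wording correction, have the Section 5.2.3 sentence on timing also name the end-of-trial pregnancy test that footnote 4 and Section 5.2.1 already require.

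**Cost.** One urine assay per woman of childbearing potential on urine already collected: at most 21 to 41 assays if every woman were tested. There is no new visit or sample. The small downside is one more result to check in the 18 h before dosing, with follow-up of any positive before allocation.

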#### **5.2.4      Electrocardiogram**

Twelve-lead ECGs (I, II, III, aVR, aVL, aVF, V1 - V6) will be recorded using a computerised electrocardiograph (Mortara ELI 250c) at the time points given in the [Flow Chart](#).

To achieve a stable heart rate at rest and to assure high quality recordings, the site personnel will be instructed to assure a relaxed and quiet environment, so that all subjects are at complete rest.

All ECGs will be recorded for a 10 sec duration after subjects have rested for at least 5 min in a supine position. ECG assessment will always precede all other study procedures scheduled for the same time to avoid compromising ECG quality.

All ECGs will be stored electronically. Electrode placement will be performed according to the method of Wilson, Goldberger and Einthoven.

All locally printed ECGs will be evaluated by the investigator or a designee. Abnormal findings will be reported as AEs (during the trial) or baseline conditions (at screening) if assessed to be clinically relevant by the investigator. Any ECG abnormalities will be carefully monitored and, if necessary, the subject will be removed from the trial and will receive the appropriate medical treatment.

Proprietary confidential information © 2020 Boehringer Ingelheim International GmbH or one or more of its affiliated companies

ECGs may be repeated for quality reasons (for instance, due to alternating current artefacts, muscle movements, or electrode dislocation) and the repeated ECG will be used for analysis. Additional (unscheduled) ECGs may be collected by the investigator for safety reasons.

